**Background:**

One major, yet poorly understood cardiovascular health risk that occurs in as many as 24% of males and 9% of females within the US population is obstructive sleep apnea (OSA). Severe OSA increases cardiovascular mortality 4 fold, and even when corrected for other risk factors increases cardiovascular mortality 3 fold. OSA can participate in both the initiation and progression of several cardiovascular diseases including sudden death, hypertension, arrhythmias, myocardial ischemia and stroke. Treatment of OSA is primarily continuous positive airway pressure (CPAP).

Diminished cardiac vagal activity is thought to be associated with many of the adverse cardiovascular consequences of OSA. Heart rate is dominated by cardioinhibitory parasympathetic activity. Parasympathetic cardiac vagal activity is typically cardioprotective and there is a high tonic level of parasympathetic and little sympathetic cardiac activity at rest. Re-establishment of cardiac vagal activity prevents arrhythmias, decreases risk of sudden death, and protects against ischemic/reperfusion injury, suggesting that restoring parasympathetic cardiac activity could be an effective therapeutic target to decrease mortality and morbidity associated with OSA.

In human volunteers intranasal administration of oxytocin significantly increases parasympathetic and decreases sympathetic cardiac control. In addition to the classic effects of oxytocin on uterine contraction and milk ejection, recent work indicates oxytocin is present in both males and females and has an important role in both behavior and cardiovascular homeostasis, particularly during anxiety and stress.

There are no clinical guidelines for the use of intranasal oxytocin in the treatment of sleep apnea but we propose that it may have a positive impact on the outcome of patients with sleep apnea, however, this research is not intended to change any clinical guidelines.

This project's specific aim will test the following hypothesis:

Intranasal oxytocin administration will blunt the deleterious hypoxia/hypercapnia induced changes in heart rate that occur during apnea in patients with OSA.

**Study Proposal:**

This proposal, based on the above detailed role of oxytocin in increasing parasympathetic and decreasing sympathetic cardiac control, will test if oxytocin administration blunts the deleterious hypoxia/hypercapnia induced changes in heart rate that occur during apnea in patients with OSA. This project will lay the groundwork and provide preliminary data to obtain NM funding to test this hypothesis more thoroughly and in larger clinical trials.

**Study Objectives:**

Primary Objective: This study will explore if intranasal oxytocin has any positive impact on blunting the deleterious hypoxia/hypercapnia induced changes in heart rate that occur during apnea in patients with OSA.

**Protocol Outline:**

To test this specific aim we will examine the changes in heart rate in a group of patients that have recently been diagnosed with OSA. The following approach will be taken for the two study cohorts listed below:

#### **Cohort A: 10 Subjects**

1. 10 subjects that have recently undergone a standard "in the sleep-lab" diagnostic polysomnography (per standard of care medical guidelines, and not for research purposes) and have been diagnosed with OSA will be recruited into the research study to assess the beneficial effects of oxytocin treatment.
2. For research: These 10 subjects will undergo another "in the sleep-lab" diagnostic polysomnography that is identical to the one that they had for standard of care to diagnose OSA. This polysomnography that is performed for research will be funded externally by the investigating group.

*If subjects are female and of child bearing potential, then their birth control method for the duration of the study will be recorded, and a urine pregnancy test will be performed prior to the PSG.*

3. Within one hour prior to the research polysomnography the subjects will be given oxytocin 40 International Units, (IU) intranasally.
4. The following 4 outcome measurements will be compared between the two sequential diagnostic polysomnographies (initial without, and second with oxytocin) in the same subjects:
  - i. basal heart rate before sleep (primary outcome)
  - ii. mean changes in heart rate with apneic and hypopneic events (primary outcome)
  - iii. apnea-hypopnea index (secondary outcome)
  - iv. percentage of time spent by the patient with oxygen saturations: > 90%, > 80% but < 90%, and < 80% (secondary outcome)

The intranasal oxytocin dose is 40 IU. The drug will be stored in the Investigational Drug Pharmacy according to the vendor's recommendations.

Polysomnography (PSG) is a comprehensive recording of the biophysiological changes that occur during sleep. It is usually performed at night, when most people sleep, though some labs can accommodate shift workers and people with circadian rhythm sleep disorders and do the test at other times of the day. The PSG monitors many body functions including brain (EEG), eye movements (EOG), muscle activity or skeletal muscle activation (EMG) and heart rhythm (ECG) during sleep. After the identification of the sleep disorder sleep apnea in the 1970s, respiratory airflow and respiratory effort indicators were added, along with peripheral pulse oximetry.

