    2. Permanent cessation of previously occurring menses as a result of ovarian failure with documentation of hormonal deficiency. Ovarian hormonal deficiency is documented by serum follicle stimulating hormone (FSH) level elevated to within the post-menopausal range based on the laboratory reference range where the hormonal assay is performed.  
OR
    3. Menopause is defined as occurring 12 months after your last menstrual period and marks the end of menstrual cycles
- Subjects who are on medications that affect cardiac autonomic function (eg. Beta blockers)
- Smokers
- Subjects who are unable to read or answer questions in the English language

The following information will be recorded on each patient before and after the use of intranasal oxytocin:

- Clinical data:
  1. Demographics — Age, gender, ethnicity, weight, BMI.
  2. Physiological data to be acquired:
    - a. Basal heart rate before sleep
    - b. Apnea-hypopnea index
    - c. Mean changes in heart rate with apneic and hypopneic events
    - d. Percentage of time spent by the patient with oxygen saturations: > 90%, > 80% but < 90%, and < 80%.
  3. Medical History Information: Current and past medical conditions, to be investigated for correlations to sleep.
  4. Standard of care sleep study data:
- The Polysomnography (PSG) monitors many body functions during sleep, including brain (EEG), eye movements (EGG), muscle activity or skeletal muscle activation (EMG), heart rhythm (ECG), respiratory airflow, thoracic and abdominal respiratory effort, body position, limb movement, and oxygen saturation using pulse oximetry. Recording and scoring is done per the standards set by the American Academy of Sleep Medicine.

All these data will be stored in a secured cabinet in the division of Pulmonary, Critical Care and Sleep Disorders offices. The primary investigator and study staff only will have access to these data. These data will lack any information that may lead to identifying any subject in the research.

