#### **Consent:**

Recruitment will occur through patient visits to the MFA, or through referrals from Walter Reed National Military Medical Center and DC Veterans Affairs providers. Introduction to the study will occur by face-to-face conversations with the subjects. The full study will be reviewed with a trained member of the research team in a private room. Subjects will be given the opportunity to ask questions and opt-out from the study during this conversation. If possible, written consent will be obtained then, but in order to avoid pressure or coercion, subjects will be provided the option to take the ICF home with them. If the subjects decide to participate they can either fax or scan and email a signed copy of the ICF to a member of the research staff. Then, either bring the wet-ink version, or wet-ink sign the ICF when they come in for their visit 1. The ICF needs to be signed prior to visit 1, as it is required for filling out the research drug prescription. During the subject's participation and during all collection and analysis activities, data will be assigned a unique study number and subsequently de-identified. No personal or demographic information

other than that specified in the study protocol will be acquired nor stored. A copy of the signed consent form will be provided to the patient

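### In Cohort A, lab and scorer differences may enter the oxytocin contrast for the event-based outcomes, because nothing requires a common lab, scoring rule or masked reader for the two nights

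*Combined protocol and SAP*

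**What the plan says.** All references are to the combined protocol and SAP.

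- **Control night.** Cohort A, item 1, enrols "10 subjects that have recently undergone a standard 'in the sleep-lab' diagnostic polysomnography (per standard of care medical guidelines, and not for research purposes"). An OSA diagnosis is a condition of entry, so this recording has already been read in routine care when the subject joins.
- **Oxytocin night.** Item 2 adds the research PSG: "These 10 subjects will undergo another 'in the sleep-lab' diagnostic polysomnography that is identical to the one that they had for standard of care". Item 4 compares the two nights, "initial without, and second with oxytocin) in the same subjects".
- **Source of subjects.** The Consent section allows recruitment at the MFA "or through referrals from Walter Reed National Military Medical Center and DC Veterans Affairs providers". The inclusion and exclusion criteria do not say where the diagnostic PSG must have been recorded.
- **Scoring.** The list of data to be recorded has one sentence, under the standard-of-care sleep study data: "Recording and scoring is done per the standards set by the American Academy of Sleep Medicine". It gives no version, hypopnea rule or reader.
- **Blinding.** The statement that technician, patient and research staff are blinded stands only under Cohort B, items 3 and 5.
- **Analysis.** Statistical Considerations names ANOVA and Fisher's exact test, with no term for lab or scorer.

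**The concern.** A paired comparison removes differences between subjects only if the measurement is the same on both occasions. Here the first reading was made for clinical diagnosis and the second belongs to the research night, and the plan does not tie the two together. A referred subject could have the first night recorded and scored at another institution. Even for a subject diagnosed in-house, nothing prevents the two nights from being read by different people, or the second from being read by someone who knows that oxytocin was given.

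Which events are marked, and where they begin and end, determines the AHI and the set of events over which heart-rate change is averaged. The latter is a primary outcome and the one closest to the stated objective. If the readings differ systematically, the difference falls between the no-drug and drug nights of the affected subjects and looks like a drug effect. If it affects every pair, it is fully confounded with treatment. If it affects only some, a comparison of subgroups within 10 subjects would be too imprecise to correct for it.

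**Working it through.** **1. Does the text secure comparability?**

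| Safeguard | What the text offers | Secured for Cohort A? |
|---|---|---|
| Same lab or equipment | the word *identical* in item 2, undefined | No |
| One hypopnea rule | general reference to the AASM standards | No |
| Same reader on both nights | no reader named for either night | No |
| Masked reader | blinding stated for Cohort B only | No |
| Statistical adjustment | none in Statistical Considerations | No |

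Cohort B, item 2, helps in reading *identical*. There the research PSG is said to match the diagnostic one provided that the diagnosis was made in a sleep lab rather than at home. On that reading the word describes the type of test, not the lab, equipment or reader.

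**2. Which outcomes are exposed?**

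- Heart-rate change at apneas and hypopneas (primary): depends on the scored events.
- AHI (secondary): counts the scored events.
- "basal heart rate before sleep (primary outcome"): read from the ECG, so it does not depend on event scoring.
- Time in saturation bands (secondary): depends on scoring little, if at all.

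Scoring differences therefore reach one of two primary and one of two secondary outcomes. A difference in equipment or in the derivation of heart rate could still touch the other two.

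**3. How large could it be?**

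The documents give no SD, effect size, alpha or power, and 10 subjects are stated without a calculation, so there is no figure to reproduce. What follows is an illustration on assumed inputs.

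- n = 10 pairs (Cohort A).
- k = number of pairs with a systematic offset (assumed 0, 2, 5, 10).
- b = size of the offset in SDs of the paired difference, in the same direction in all affected pairs (assumed 0.25, 0.5, 1.0).
- No true drug effect; two-sided 5% paired t-test. With two nights per subject this equals a repeated-measures ANOVA.

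Bias = k × b / n. For example, 5 × 0.5 / 10 = 0.25 SD.

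Test statistic: t = mean difference / (SD of differences / √10), on 10 − 1 = 9 degrees of freedom. False-positive rate from 200,000 simulated cohorts:

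| k | b = 0.25: bias, rate | b = 0.5: bias, rate | b = 1.0: bias, rate |
|---|---|---|---|
| 0 | 0, 4.9% | 0, 5.1% | 0, 5.0% |
| 2 | 0.05, 5.0% | 0.10, 5.5% | 0.20, 6.5% |
| 5 | 0.125, 6.3% | 0.25, 9.9% | 0.50, 21.6% |
| 10 | 0.25, 10.9% | 0.50, 29.3% | 1.00, 80.3% |

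The rows with k = 2 and 5 suit outside recordings in some subjects. The row with k = 10 suits a difference between the clinical and research readings, or unmasked reading, that runs through every pair. For scale, 10 pairs have 80% power for a true difference of about 1.0 SD (0.996), which agrees with the last cell.

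**The case against.** The strongest reply is that the protocol states its intention: the two PSGs are to be identical, and recording and scoring follow a published standard. A referral also says nothing about where the diagnostic PSG was done, and the recruitment sentence is not specific to Cohort A. Further, the data list places heart-rate change at events under physiological data to be acquired before and after oxytocin, apart from the standard-of-care sleep data. That is compatible with the study deriving it in the same way on both nights.

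Much of this stands. A reader might infer that outside diagnostic PSGs will be used, and that lab and scorer differences therefore do enter the contrast. The documents do not support that: they leave it possible and state neither. A reader might also infer that a clinical scorer reads the first night and a study scorer the second; no section says who reads either. It would also be wrong to extend a scoring effect to all four outcomes, or to treat any figure as the plan's own bias. Offsets from two institutions could also partly cancel, which the illustration does not allow for.

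What does not stand is that the intention is enough. A shared standard is not a shared or masked reader, and deriving heart rate alike on both nights needs raw signals that no section secures.

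It is also fair to say that Cohort A is small and exploratory, and that its fixed order, lack of placebo, open treatment and unstated interval between nights are certain from the text and matter more. That limits the weight of this point. It does not make separate, open scoring preferable to common, masked scoring.

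**Conclusion.** The point holds as a gap in the plan. For the two event-based outcomes of Cohort A, lab and scorer differences may enter the comparison of the oxytocin night with the diagnostic night, because comparability is asserted but not secured. The size cannot be obtained from the documents. On the assumed offsets, the result runs from no effect (no pair affected, or no offset) to a false-positive rate of about 80% (all 10 pairs shifted by 1 SD in the same direction). These figures show sensitivity and are not an estimate. The conclusion rests on the absence of any rule on lab, hypopnea definition, reader or masking in Cohort A, and on the dependence of the two outcomes on scored events. It does not rest on any assumption about how many subjects are referred. The change is worth making because it is cheap, but it does not turn the Cohort A contrast into an unconfounded estimate of the drug effect.

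**What to change.** In Cohort A, item 2, say what *identical* requires:

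- The diagnostic PSG was recorded in the study sleep-lab, or its raw signals are available to the study. Record which lab it came from.
- One reader from the existing sleep-lab or study staff scores both tracings of each subject together, under one stated AASM hypopnea rule, with date and treatment labels removed.
- These scores, not the clinical report, are used for heart-rate change at events and for AHI.
- Heart rate and saturation measures are derived with the same algorithm on both nights.

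Cost: 10 subjects × 2 nights = about 20 tracings to score and a short protocol addition, with no new procedure for subjects. Provided that the raw signals are kept, the scoring can be done after recording and before analysis. The downside is the loss from Cohort A of referred subjects whose raw diagnostic recording cannot be obtained. The fixed order and the absence of placebo remain and should be stated as limits when Cohort A is reported.

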#### **Cohort B: 40 Subjects**

Once enrollment in Cohort A is complete, then enrollment into Cohort B will begin.

1. 40 Subjects that have recently undergone either a standard "in the sleep-lab" diagnostic polysomnography (per standard of care medical guidelines, and not for research purposes) or an "at home" PSG test and have been diagnosed with OSA will be recruited into the research study where we will assess the beneficial effects of oxytocin treatment.
2. For research: These 40 subjects will undergo an "in the sleep-lab" diagnostic polysomnography that would be identical to the one they had for standard of care medical guidelines if they were diagnosed with OSA "in the sleep-lab". This research

polysomnography should be performed within **4 weeks** of their OSA diagnosis PSG. This PSG that is being performed for research will be funded externally by the investigating group.

*If subjects are female and of child bearing potential, then their birth control method for the duration of the study will be recorded, and a urine pregnancy test will be performed prior to the PSG.*

3. Subjects will be randomized by the Investigational Drug Services Pharmacy of the MFA to be administered either Oxytocin (40 IU) or placebo within one hour prior to beginning the study polysomnography.
  - a. Both the polysomnography technician, the patient, and all research staff will be blinded to this randomization. The only un-blinded personnel will be the IDS pharmacy staff.
4. Subjects will then return within **4 weeks** to have a **second research study** polysomnography performed by the sleep-lab. This polysomnography that is being performed for research will be funded externally by the investigating group.
5. Subjects will be administered the intervention that *they did not receive* during the first research PSG study within one hour prior to beginning the second polysomnography. Either Oxytocin (40 IU) or placebo.
  - a. Both the polysomnography technician, the patient, and all research staff will be blinded to this randomization. The only un-blinded personnel will be the IDS pharmacy staff.

*For example: If at study polysomnography 1 a subject is randomized to receive placebo 1 hour prior to the start of the polysomnography, then at study polysomnography 2 the subject will be administered oxytocin (40 IU) 1 hour prior to the start of the polysomnography.*

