#### **Costs to Subjects:**

There will be no additional costs to the subjects to participate in this protocol. The routine medical care for all tests and medications associated with the diagnosis and treatment of sleep apnea will be the responsibility of the patient.

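### OSA treatment started between the compared sleep studies is neither recorded nor handled in the analysis, so a carry-over effect on heart rate could be read as an oxytocin effect in Cohort A

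*Combined protocol and SAP*

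**What the plan says.** Both cohorts recruit people recently diagnosed with OSA. The Background states: "Treatment of OSA is primarily continuous positive airway pressure (CPAP"). Under Costs to Subjects the protocol adds: "The routine medical care for all tests and medications associated with the diagnosis and treatment of sleep apnea will be the responsibility of the patient".

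**Cohort A (10 subjects).** Item 2 calls for a second in-lab "diagnostic polysomnography that is identical to the one that they had for standard of care to diagnose OSA". Item 4 compares the two nights ("initial without, and second with oxytocin) in the same subjects". The order is fixed, there is no control, and no maximum interval is given beyond the requirement that the diagnosis be recent.

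**Cohort B (40 subjects).** Item 2 calls for a "diagnostic polysomnography that would be identical to the one they had for standard of care medical guidelines", where the diagnosis was made in the lab, within 4 weeks of the diagnostic study. Items 3 to 5 randomise the order of oxytocin and placebo over two research nights, the second within a further 4 weeks. Item 6, however, describes the comparison as the standard-of-care night against the research night with oxytocin.

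**What is controlled or recorded.** The only exclusion about other treatment is "Subjects who are on medications that affect cardiac autonomic function (eg. Beta blockers"), with no written re-check at later nights. The list of recorded data covers demographics, physiological measures, current and past medical conditions, and sleep-study data. It has no entry for CPAP or other OSA treatment, its start date or its use. Statistical Considerations names ANOVA and Fisher's exact test and mentions no covariate, period or sequence term.

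**The concern.** A within-subject comparison credits the drug with whatever differs between the two nights. It works only if the subject's underlying state is otherwise comparable. Newly diagnosed patients are the group most likely to begin treatment during the weeks in question.

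Both primary outcomes are heart-rate measures, and the Background itself links OSA to reduced cardiac vagal activity. On the protocol's own reasoning, treating OSA could therefore affect these outcomes. If such an effect outlasts the treated nights, Cohort A cannot separate it from oxytocin. Because treatment status is not collected, the analyst could not reliably tell from the study data whether this had happened. The study is meant to supply preliminary data for larger trials, so a misattributed signal would be carried forward.

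**Working it through.** The plan states no SD, effect size, power or treatment uptake, so it has no figure to reproduce. The inputs below are assumptions, apart from the cohort sizes (10 and 40).

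- p = share of subjects who start OSA treatment between the two compared nights: 25% to 75%.
- d = resulting carry-over shift in heart rate: 0 to 4 bpm. Zero is included because the documents do not show that any carry-over exists.
- True oxytocin effect: 0.

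**Cohort A.** The oxytocin night always comes second, so bias = p × d.

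- Lower end: d = 0 gives 0 bpm for any p.
- Middle: 0.50 × 3 = 1.5 bpm.
- Upper end: 0.75 × 4 = 3.0 bpm.

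To show what the middle case does to a test, take a two-sided 5% paired t-test with n = 10. The variance of the difference is SD² + d² × p(1−p), and the noncentral t distribution gives the false-positive rate. For p = 0.5 and d = 3:

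| Assumed SD of difference | False-positive rate |
|---|---|
| 4 bpm | 16.9% |
| 6 bpm | 10.6% |
| 8 bpm | 8.2% |

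With d = 0 the rate is the nominal 5%. With p = 0.25, d = 1 and SD 5 it is 5.2%.

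**Cohort B, oxytocin against placebo.** Treatment begun before the first research night and kept stable is present on both nights and largely cancels. Only a start or change between the two research nights matters. It adds d to the later night, which is the oxytocin night in one sequence and the placebo night in the other.

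- Expected bias with equal sequences: 0.
- Added variance of the within-subject difference, no period term: p × d². With p = 0.5, d = 3 and SD 5: 0.5 × 9 = 4.5; 4.5/25 = +18%; √1.18 = 1.086, about +9% in SD.
- With a period term: p(1−p) × d² = 0.25 × 9 = 2.25; 2.25/25 = +9%; √1.09 = 1.044, about +4% in SD.
- Unequal sequences without a period term: bias = p × d × (n placebo-first − n oxytocin-first)/N. A 24/16 split gives 1.5 × 8/40 = 0.30 bpm.

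**Cohort B, item 6 read literally.** The untreated reference is the diagnostic night and the oxytocin night always follows it, so bias is again p × d. With n = 40, p = 0.5, d = 3 and SD 6, the same test gives a false-positive rate of 32%. This is higher than in Cohort A because the larger sample detects the same 1.5 bpm bias more readily.

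**The case against.** **The costs passage is about who pays.** This is correct. It presupposes that OSA is treated but gives no timing. A reader might infer that a site following the plan would necessarily compare an untreated night with one after weeks of treatment. The documents support only that it could.

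**An identical diagnostic study means no CPAP.** For the recording night this is a fair reading, and the outcomes require apneic and hypopneic events to be scored. It rules out the strongest form of the confound. It says nothing about preceding nights or other treatments, and in Cohort B the word identical applies only to subjects diagnosed in the lab.

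**The crossover protects Cohort B.** It largely does, for an oxytocin-placebo contrast. A reader might treat the whole span of about 8 weeks (4 + 4) as exposure, or infer bias in the randomised contrast. Neither follows: only the interval between the two research nights counts, and its effect is mainly modest extra variance. The protection is lost if item 6 is applied as written.

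**Cohort A is exploratory and uncontrolled anyway.** This also stands. Time, night-to-night and expectation effects are confounded with oxytocin there regardless, and recording OSA treatment would not make the result attributable to the drug. It would still let readers see whether one foreseeable alternative explanation applies.

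**Conclusion.** The point holds as a gap in recording and analysis. Nothing in the protocol covers OSA treatment started between the compared nights, although the population and the reliance on usual care make it foreseeable.

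In Cohort A the possible bias is 0 to 3 bpm under the assumed ranges, all of it on the oxytocin night. Its true size and direction are unknown. In Cohort B the consequence depends on which comparison is meant: mainly added variance for oxytocin against placebo, or the same confounding as Cohort A under item 6 as written. The documents do not support saying that treatment did or would distort the results, only that it could and that the study data would not reliably show it.

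**What to change.** 1. At each research night, record whether CPAP or any other OSA treatment has started since the diagnostic study (type, start date, recent use), and any new medication affecting cardiac autonomic function.
2. Keep all subjects in the primary paired comparison. Prespecify a sensitivity analysis by whether treatment status was the same on both compared nights, and interpret Cohort A's result in its light.
3. Reconcile Cohort B item 6 with the crossover in items 3 to 5, so that the two nights being compared are stated without contradiction.

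Restricting the primary comparison to pairs with unchanged status is tempting but not advised. It selects on an event after enrolment (after randomisation, if between Cohort B's research nights). At p of 25-75% it would leave 10 × 0.75 = 7.5 down to 10 × 0.25 = 2.5 pairs in Cohort A, roughly 2 to 8.

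The cost is a few case-report fields at visits already planned, one extra analysis and a wording correction. Nobody's treatment is delayed or changed.

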#### **Statistical Considerations:**

ANOVA and Fisher's Exact Test will be done to compare multiple means from repeated measures. A consultation with an expert statistician will also be considered for data analysis.

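### Cohort A always gives oxytocin on the second night and has no placebo, so its two primary outcomes cannot separate the drug from the night

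*Combined protocol and SAP*

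**What the plan says.** All references are to the combined protocol and SAP.

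- **Comparator night.** Under Cohort A, item 1, the no-drug night is a diagnostic study already done in routine care: "per standard of care medical guidelines, and not for research purposes) and have been diagnosed with OSA will be recruited". No interval to the research night is set for this cohort; Cohort B has a limit of 4 weeks.
- **Treatment night.** Item 3 gives every subject the drug: "Within one hour prior to the research polysomnography the subjects will be given oxytocin 40 International Units, (IU) intranasally".
- **Contrast.** Item 4 compares the two nights in a fixed order: "initial without, and second with oxytocin) in the same subjects".
- **Outcomes.** Item 4 lists "basal heart rate before sleep (primary outcome") and "mean changes in heart rate with apneic and hypopneic events (primary outcome"). Two further outcomes are secondary.
- **Purpose.** Item 1 says the subjects "will be recruited into the research study to assess the beneficial effects of oxytocin treatment".
- **Analysis.** Statistical Considerations says "ANOVA and Fisher's Exact Test will be done to compare multiple means from repeated measures". It gives no significance level, no term for night or order, and no separate treatment of the two cohorts.

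Randomisation, placebo, crossover and blinding are described under Cohort B (items 3 to 5) and not under Cohort A. Cohort B item 6, however, defines that cohort's comparison as the routine-care diagnostic study against a later research study with oxytocin. Placebo does not appear in it.

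**The concern.** In Cohort A, being on oxytocin and being on the second night are the same variable. The two nights may differ for other reasons: the subject now knows the laboratory, time has passed, and the subject knows that an active drug was given. Basal heart rate is measured while the subject is awake, so familiarity and expectation could plausibly affect it. Each such influence goes into the difference that the plan would read as the effect of oxytocin.

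At stake is what may be concluded. The plan calls these outcomes primary, and the Study Proposal section says the results are to support funding for larger trials. A shift between nights, with no drug effect at all, could look like a positive primary result and feed that decision.

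**Working it through.** The plan states no power, significance level, standard deviation or effect size, so it has no figure to reproduce. The check has three steps.

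**1. What Cohort A can estimate.** Let δ be the oxytocin effect and π the shift from first to second night from all other causes. Every subject has the same order, so the mean paired difference estimates δ + π. No subject receives oxytocin first, and none has a second night without it. Only the sum can be estimated. A covariate, an ANOVA term or more subjects would not change that.

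**2. How large the consequence could be.** Inputs:

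- n = 10, from the heading "Cohort A: 10 Subjects".
- Paired t-test, equivalent to a two-night repeated-measures ANOVA.
- Two-sided 5% level (assumed).
- δ = 0 (assumed).
- π = d standard deviations of the paired difference (assumed range).

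The test rejects when |t| exceeds 2.262 on 9 degrees of freedom. Under the shift, t is noncentral with noncentrality d√10. For at least one of two primary outcomes the rate is 1 − (1 − p)², assuming independence and the same shift in both.

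| Assumed shift d | d√10 | False positive, one outcome | At least one of two |
|---|---|---|---|
| 0 | 0 | 5.0% | 9.75% |
| 0.2 | 0.632 | 8.8% | 16.8% |
| 0.3 | 0.949 | 13.6% | 25.4% |
| 0.5 | 1.581 | 29.3% | 50.0% |
| 0.8 | 2.530 | 61.6% | 85.3% |

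Both outcomes come from the same nights in the same subjects, so independence is doubtful and the single-outcome column is the safer one. Splitting the level to 2.5% per outcome does not cure the problem: at d = 0.5 the rate per outcome is still 19.2%. Nor does a larger sample: the same fixed-order contrast in 40 subjects at d = 0.5 rejects 86.9% of the time.

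**3. Whether the Cohort B design removes the problem.** Take the difference, second minus first research night. Its mean is π + δ for placebo then oxytocin, and π − δ for oxytocin then placebo. Half the difference between the sequences is ½[(π + δ) − (π − δ)] = δ, so the night shift cancels, assuming no carry-over.

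This was simulated for 40 subjects, 20 per sequence (equal split assumed, 50,000 runs), with δ = 0 and shifts of 0, 0.5, 0.8 and 1.0 SD. The period-adjusted test rejected 5.1%, 4.9%, 4.9% and 4.9% of the time. A paired test without a period term rejected 5.1%, 2.8%, 1.3% and 0.6%. It is unbiased but conservative, because the night shift enters its error variance. That is the reason for asking for the period term.

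**The case against.** The strongest reply is that Cohort A is a small lead-in and the sponsor has already supplied the remedy. Study Objectives describes the work as exploratory, Study Proposal as preliminary, and Background disclaims any intent to change guidelines. Cohort B then enrols 40 subjects in a randomised, blinded, placebo-controlled crossover. This limits the weight of the point. It does not remove it: Background and Study Proposal also speak of testing the hypothesis, nothing calls Cohort A descriptive or a pilot, and two of its outcomes are labelled primary. Cohort B is a safeguard only if its placebo contrast is the one analysed, and item 6 does not say so.

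Several limits on the point stand:

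- The sizes and direction of any night effect are not in the documents. The 62% belongs to an assumed shift of 0.8 SD.
- The protocol does not use the term open-label for Cohort A. It is inferred, because every subject receives oxytocin and blinding is described only for Cohort B.
- Selection on the diagnostic night bears mainly on the apnea-hypopnea index, a secondary outcome, and much less on the heart-rate outcomes.
- Study Treatment mentions oxytocin or placebo at the second sleep study without naming a cohort. That does not fit Cohort A item 3 and cannot be read as giving Cohort A a control; the two sections should be reconciled.

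A reader might go further and infer that the 10 pairs will be pooled with Cohort B and bias the randomised result. The documents do not support this. They do not plan pooling; each cohort has its own comparison list, and Cohort B enrols only after Cohort A is full. Pooling is merely not excluded. Any figure for it would also presuppose an oxytocin-versus-placebo analysis in Cohort B that item 6 does not state.

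**Conclusion.** The point holds as a limit on inference. In Cohort A, drug and night are fully confounded for both primary outcomes, and no analysis of that cohort can separate them. This follows from the design alone and needs no assumption about size. The illustrative false-positive rates of about 9%, 14%, 29% and 62% per outcome rest on a paired t-test, a two-sided 5% level, no drug effect and assumed shifts of 0.2, 0.3, 0.5 and 0.8 SD.

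A reader might infer that a night effect is present, or that the sponsor will credit any shift to oxytocin. The documents establish neither: they give no data on night effects and no success criterion for Cohort A. A single-group lead-in is legitimate if its claims are limited. With 10 subjects, an exploratory aim and a randomised cohort to follow, the point is worth acting on because the correction is cheap, and it is no reason to redesign or drop Cohort A.

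**What to change.** Two changes of wording, which must be made together.

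1. **Cohort A, item 4.** Remove the primary and secondary labels. State that this cohort provides paired mean differences with 95% confidence intervals for feasibility and variance, that no significance test or efficacy claim will be made, and that it is analysed separately from Cohort B. Note beside the intervals that they cover drug and night effects combined.
2. **Cohort B, item 6.** Replace the comparison of the routine-care study with an oxytocin study, which does not match the crossover in items 3 to 5. Define the primary inference as the randomised within-subject contrast of oxytocin with placebo between the two research nights, with a period term in the model.

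Changing Cohort A alone would leave item 6 contradicting the new text. No extra subjects, nights or procedures are needed. The sponsor gives up an early significance claim from 10 subjects.
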